### **5.3 REPORTING PROCEDURES**

All adverse events should be reported. Depending on the nature of the event the reporting procedures below should be followed. Any questions concerning adverse event reporting should be directed to the Chief Investigator in the first instance.

#### **5.3.1 Non serious AEs**

All such events, whether expected or not, should be recorded.

#### **5.3.2 Serious AEs**

An SAE form should be completed and faxed to the Chief Investigator within 24 hours. However, relapse and death due to heart failure, and hospitalisations for elective treatment of a pre-existing condition do not need reporting as SAEs.

All SAEs should be reported to the London - Brent Research Ethics Committee where in the opinion of the Chief Investigator, the event was:

- 'related', ie resulted from the administration of any of the research procedures; and
- 'unexpected', ie an event that is not listed in the protocol as an expected occurrence

Reports of related and unexpected SAEs should be submitted within 15 days of the Chief Investigator becoming aware of the event, using the NRES SAE form for non-IMP studies. The Chief Investigator must also notify the Sponsor of all SAEs.

Local investigators should report any SAEs as required by their Local Research Ethics Committee, Sponsor and/or Research & Development Office.

Contact details for reporting SAEs  
email: [[contact]](mailto:[contact]) and [[contact]](mailto:[contact])  
Please send SAE forms to: [name]  
[contact] [name] (Mon to Fri 09.00 – 17.00)

## **6. ASSESSMENT AND FOLLOW-UP**

### **SCREENING ASSESSMENTS**

None other than entry criteria.

## **BASELINE ASSESSMENTS**

- 1) Prolonged ECG (up to 7 days) monitoring using a patch-electrode
- 2) Symptom Questionnaire
- 3) Evaluation of NYHA functional class.
- 4) Physical examination including blood pressure
- 4) 6-min corridor walk distance for patients who are willing and able.
- 5) Most recent, clinically indicated, haematology, biochemistry, ECG and Echo results (these will not be repeated for research purposes).

## **TREATMENT PROCEDURE**

Not applicable. No protocol driven treatment. Patients will be treated according to guidelines if electrocardiographic abnormalities are identified.

### **10.4 SUBSEQUENT ASSESSMENTS**

We will contact patients every 6 months by telephone or post (according to their preference) or opportunistically at NHS clinics to identify hospitalizations. We will ensure that the patient is still alive just before making remote contact by checking the hospital electronic record and with the GP reception staff. Hospitalizations and deaths will also be identified through electronic patient records.

#### **Definition of end of study**

The end of the study will occur when the last patient enrolled has been followed for 5 years. A long-term extension is considered. [name] fellowship is only for 2 years and other personnel are required for longer follow-up.

## **7. STATISTICS AND DATA ANALYSIS**

The design is a prospective, observational trial with two cohorts of 200 patients; one in sinus rhythm and the other in atrial fibrillation.

This should generate in excess of 50 deaths in the year following observation assuming a substantial proportion of patients are enrolled soon after an episode of worsening heart failure. We will investigate which measured variables predict overall mortality, sudden death and out-of-hospital sudden death with a particular focus on electrocardiographic findings. We will investigate mode of death, if necessary, by contacting medical and nursing staff (including the patients GP) who attended the patient around the time of death.

#### **SAMPLE SIZE AND RECRUITMENT**

The sample size is based on the precision of the estimated prevalence of serious arrhythmia. As this is, surprisingly, virtually unknown for similar contemporary populations we intend to study with the proposed technology, this should be considered a pilot. Assuming the incidence of events is low, medium or high (eg:- 5%, 25% or 50%), 200 patients provides a precision around these estimates of approximately  $\pm 5\%$ ,  $\pm 10\%$  and  $\pm 12\%$  with 90% power.

We aim to recruit this population over 12 months – this will entail enrolling about two patients every working day. Due to the small imposition on the patient, the lack of many exclusion criteria and the potential for referrals from across North-West London we believe this is feasible.

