## 3. STUDY DESIGN

Observational study; non-commercial.

Duration 5 years (clinical phase 18 months).

400 patients with heart failure

We will include patients with heart failure. We are investigating the prevalence of subclinical arrhythmias in this population and their association with clinical outcomes. The patient will have a 7-14 days ambulatory ECG after which we will follow them up every 6 months for up to 5 years. At each time point, we will contact patients by phone or post and ask them if they have any hospital admissions. Every effort will be made to ensure that we know the patients

mortality status, before each planned follow up. We will call the patient's GP prior to making any direct contact with the patients.

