## STATISTICAL ANALYSIS PLAN

The design is a prospective, observational trial with two cohorts of 200 patients; one in sinus rhythm and the other in atrial fibrillation.

Data will be expressed as proportions for categorical data and median with quartile range for continuously distributed data.

Loss to follow-up for the primary or secondary endpoints is not anticipated. It is anticipated that monitoring data may not be acquired in some patients. This will be recorded. Missing data will not be imputed. Monitored events will be expressed as a rate per day of monitoring data and per patient regardless of the duration of monitoring.

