### Primary endpoint analysis

The primary analysis is the incidence rate of the primary composite endpoint.

We will investigate factors associated with the primary point. Pre-specified variables include: age, sex, NYHA class, body mass index, heart rate measured at examination, left ventricular ejection fraction, presence of calcific aortic or mitral valve disease, left atrial volume, conduction abnormalities on the 12-lead ECG, serum potassium and serum creatinine.

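### The ±5, ±10 and ±12 point margins quoted for 200 patients are not prevalence margins at 90%, 95% or 99% confidence, and no confidence level is stated

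*Combined protocol and SAP*

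**What the plan says.** In Section 7, under Sample size and recruitment, the basis is explicit: "The sample size is based on the precision of the estimated prevalence of serious arrhythmia". For example rates of 5%, 25% and 50%, "200 patients provides a precision around these estimates of approximately" ±5%, ±10% and ±12%, qualified by 90% power. The same section describes the prevalence as practically unknown and the study as a pilot.

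The figure of 200 is one cohort. Section 3 gives "400 patients with heart failure" in total, and the Statistical analysis plan describes "two cohorts of 200 patients; one in sinus rhythm and the other in atrial fibrillation".

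No confidence level, alpha, sidedness, null value, test or interval method appears in the sample-size section or in the analysis plan. On reporting, the plan says "Data will be expressed as proportions for categorical data and median with quartile range for continuously distributed data", and the Primary endpoint analysis says "The primary analysis is the incidence rate of the primary composite endpoint". Neither mentions an interval.

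Section 7 also says of the two cohorts "This should generate in excess of 50 deaths in the year following observation". That is an expectation about event numbers, not a second derivation of the precision.

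**The concern.** Precision and power are different things. A ± figure around an estimated proportion is fixed by the sample size, the proportion and a confidence level; power belongs to a test of a hypothesis. The sentence gives a ± figure with power and no confidence level, so the reader cannot tell what the figure is.

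The values also look too large for n = 200. Near 50%, the familiar 95% margin for 200 patients is about 7 points, not 12.

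Because precision is the stated basis for the sample size and the prevalence is said to be almost unknown, the width of the interval is a main product of this study and an input to the later research it is meant to inform. As written, the plan promises a precision at no identifiable level and does not commit to reporting it.

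**Working it through.** **Inputs.** n = 200 (one cohort), p = 5%, 25%, 50%, and stated margins of 5, 10 and 12 points, all from Sample size and recruitment. The confidence level is not in the documents, so 90%, 95% and 99% are all tried.

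**Standard error.** SE = √(p(1−p)/200):
- p = 5%: √(0.05 × 0.95/200) = 1.541 points
- p = 25%: √(0.25 × 0.75/200) = 3.062 points
- p = 50%: √(0.50 × 0.50/200) = 3.536 points

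**Can the plan's figures be reproduced as ± margins?** Half-width = z × SE, in percentage points:

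| Quantity | 5% | 25% | 50% |
|---|---|---|---|
| Stated margin | 5 | 10 | 12 |
| Half-width, 90% (z = 1.645) | 2.54 | 5.04 | 5.82 |
| Half-width, 95% (z = 1.960) | 3.02 | 6.00 | 6.93 |
| Half-width, 99% (z = 2.576) | 3.97 | 7.89 | 9.11 |

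They cannot. Stated margin divided by computed half-width is 1.97–2.06 at 90%, 1.66–1.73 at 95% and 1.26–1.32 at 99%.

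**What level do the stated figures imply?** 5/1.541 = 3.24, 10/3.062 = 3.27 and 12/3.536 = 3.39 standard errors, that is, two-sided confidence of 99.88%, 99.89% and 99.93%.

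**Other interval methods.** Wilson half-widths are 3.1/6.0/6.9 at 95% and 4.2/7.8/9.0 at 99%. The larger arm of the Clopper-Pearson interval is 4.0/6.6/7.1 at 95% and 5.4/8.7/9.3 at 99%. None gives 5/10/12. Using all 400 patients moves further away: 2.1/4.2/4.9 at 95%.

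**Quantities that do come close.**
- Full width of a 90% interval, 2 × 1.645 × SE = 5.07, 10.07, 11.63. This rounds to 5, 10, 12, but a full width is not a ± figure.
- Difference detectable in a one-sample test, two-sided 5%, 90% power, (1.960 + 1.282) × SE = 5.00, 9.93, 11.46. This fits the first two figures well and the third loosely.

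**Sample size the stated margins would need.** n = z²p(1−p)/d². At 95%: 72.99, 72.03 and 66.69, so 73, 73 and 67 patients. Taken literally at 95%, the stated precision does not explain a choice of 200.

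**Asymmetry at a low rate.** The 95% Wilson interval for 10/200 is 2.74–8.96%, or −2.26/+3.96 points. The stated 5 points still exceed the upper arm, by 5/3.96 = 1.26. At 99% the Wilson upper arm is 5.61 points, so for that single arm 5 is not an overstatement.

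**The case against.** The strongest reply is that the text says power and should be read that way. With an unstated two-sided alpha of 5%, the detectable differences are 5.00, 9.93 and 11.46, against figures the plan calls approximate. On that reading the numbers are about right and the fault is labelling, not calculation. It can be added that 99.9% half-widths (5.07, 10.08, 11.63) also round to 5/10/12, that the plan calls the study a pilot and its rates examples, and that no test or stopping rule depends on the figures.

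Part of this stands. The numbers are not arbitrary, and a slip in arithmetic cannot be told apart from a mislabelled quantity. It does not rescue the sentence. The plan itself calls the figures a precision and writes them with ±. A detectable difference is neither; it needs an alpha and a null value that are not given, and it belongs to a test the analysis plan does not contain. Nor can a level of 99.9% be assumed when none is stated. Approximation cannot turn 3/6/7 into 5/10/12: the factor is nearly constant, which points to a different quantity rather than loose rounding.

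One limit is accepted: the remark that the error is conservative holds at 90% and 95%, but not for the upper arm of the 99% Wilson interval at 5%.

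**Conclusion.** The point holds. As margins around a prevalence from 200 patients, ±5, ±10 and ±12 are wrong at 90%, 95% and 99% confidence: about twice the half-width at 90%, 1.7 times at 95% and 1.3 times at 99%. No confidence level is given, and power cannot stand in for one. Which quantity was intended cannot be settled from the documents.

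This is a reporting error, not a shortfall in size. At 95% confidence each cohort gives roughly ±3, ±6 and ±7 points, tighter than the plan claims. The comparison rests on the normal approximation, on 200 patients per cohort with usable monitoring data, and on a per-patient proportion as the estimate.

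**What to change.** In Sample size and recruitment, delete the power phrase, state the confidence level and interval method, and say that the ± figures are half-widths. Assuming 95%, the sentence could read: *With 200 patients per cohort, observed prevalences of 5%, 25% and 50% have 95% Wilson intervals of 2.7–9.0%, 19.5–31.4% and 43.1–56.9% (normal-approximation half-widths of about 3.0, 6.0 and 6.9 percentage points; the interval at 5% is asymmetric).* If 90% was meant, the half-widths are about 2.5, 5.0 and 5.8. If a test was intended, name it with its null value and alpha, call the figures detectable differences, and add the test to the analysis plan.

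In Primary endpoint analysis, add that the proportion of patients meeting each co-primary endpoint is reported by cohort with an interval at the chosen level. The Wilson interval suits that per-patient proportion; event rates per monitored day would need a different interval.

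The cost is one sentence in each section, with no change to enrolment.

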## ENDPOINTS

### Primary endpoint

1. Identification of an arrhythmia for which there is a Class I or IIa recommendation for treatment with medication or devices
2. Either the above or one or more of the following (expanded endpoint) even if it does not otherwise meet guideline-indication for treatment:-
  - Sinus bradycardia  $\leq 30$ bpm for  $\geq 1$ one minute
  - High-degree atrioventricular (AV) block (3rd degree or Mobitz Type I or II)
  - Pauses lasting  $\geq 3$  seconds (either sinus or AV block)
  - Frequent ventricular ectopy defined as  $>1,000$  ectopic beats per day.
  - Ventricular tachycardia with rate  $\geq 100$  bpm for  $\geq 5$  beats.

### Secondary endpoints

Relationship of the above to all-cause mortality, cardiovascular mortality, hospitalization for heart failure or arrhythmia, implantation of a device with a capacity to pace the heart.

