### 1.2 RATIONALE FOR CURRENT STUDY

The purpose of this study is to quantify the total arrhythmia burden (both slow and fast rhythms) in patients with heart failure using a wearable patch that can monitor the heart for up to 14 days. We then intend to follow the patients' progress over the next 5 years. We may find serious rhythm problems, in which case we will recommend treatment according to expert international guidelines (Guidelines on pacing 2013 and on sudden death 2015). This information will provide information on the incidence of severe arrhythmias that guidelines indicate should be treated and of the association of less severe arrhythmias (or their absence) with prognosis. This should improve patient care and inform the design of further research.

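### The heart failure or arrhythmia hospitalisation endpoint does not exclude planned admissions, so scheduled treatment of an arrhythmia found on the patch can count as an outcome of that arrhythmia

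*Combined protocol and SAP*

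**What the plan says.** The hospitalisation outcome appears in the Study Summary, in section 3.1 and under Secondary endpoints in section 7, as part of a list that includes "hospitalization for heart failure or arrhythmia, implantation of a device with a capacity to pace the heart". In none of the three places is there a qualifier for urgency or main cause.

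Collection is equally broad. Section 3 says that at each six-monthly contact "we will contact patients by phone or post and ask them if they have any hospital admissions". Section 10.4 adds that "Hospitalizations and deaths will also be identified through electronic patient records". Neither describes a field for planned versus unplanned admission, or a rule for assigning the cause of an admission.

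Elective admissions are mentioned once, in section 5.3.2, where "hospitalisations for elective treatment of a pre-existing condition do not need reporting as SAEs". That exemption concerns safety reporting and is not carried over to the outcome.

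Three statements link the monitoring result to later care:
- Section 1.2 says that serious rhythm problems may be found, "in which case we will recommend treatment according to expert international guidelines".
- The Treatment Procedure paragraph of section 6 says that "Patients will be treated according to guidelines if electrocardiographic abnormalities are identified".
- The first co-primary endpoint is "Identification of an arrhythmia for which there is a Class I or IIa recommendation for treatment with medication or devices".

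**The concern.** The secondary objective relates arrhythmia burden to clinical events, and section 1.2 presents this as information on prognosis. An emergency admission with ventricular tachycardia is evidence of deterioration. An admission by appointment to treat an arrhythmia that the patch revealed is evidence that the patch was read and acted on. The endpoint wording does not separate the two.

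This goes beyond an untidy definition because the possible miscount is tied to the exposure. Patients classed as positive on the first co-primary endpoint are, by definition, those for whom treatment is recommended, and the plan says they will be treated. Any of that care delivered through a scheduled admission would add events mainly to the positive group. A finding with no effect on prognosis could then appear prognostic. Leaving the point open also means that the counting rule could be settled after the admissions have been seen.

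**Working it through.** **Plan's own figure.** There is none to reproduce. The documents give no hospitalisation rate and no share of planned admissions. The precision figures under Sample Size and Recruitment concern arrhythmia prevalence only.

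**Text check.** Side by side: the endpoint is unqualified in all three places; collection covers any admission; the only elective exemption is for SAE reporting; and patch findings lead to treatment. Section 1.1 names interventions for arrhythmias separately from hospitalisation, and the secondary list names device implantation separately. Neither says that an admission for an intervention is left out of the hospitalisation count.

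**Illustration.** Inputs:
- From the documents: 400 patients in all (two cohorts of 200), and 25%, the middle of the plan's three example frequencies. This gives 100 arrhythmia-positive and 300 arrhythmia-negative patients.
- Assumed: unplanned admission risk *b*, the same in both groups, so the true ratio is 1.0.
- Assumed: planned rhythm-admission rates *q1* in positives and *q0* in negatives, independent of unplanned admission.

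The apparent risk is p = b + (1 − b)q in each group, and the apparent ratio is [b + (1 − b)q1] / [b + (1 − b)q0].

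At b = 30%:

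| q1 | q0 | Risk, positives | Risk, negatives | Ratio |
|---|---|---|---|---|
| 5% | 0% | 0.30 + 0.70 × 0.05 = 0.335 | 0.300 | 1.12 |
| 10% | 0% | 0.30 + 0.70 × 0.10 = 0.370 | 0.300 | 1.23 |
| 25% | 10% | 0.30 + 0.70 × 0.25 = 0.475 | 0.370 | 1.28 |
| 10% | 10% | 0.370 | 0.370 | 1.00 |
| 10% | 25% | 0.370 | 0.475 | 0.78 |

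**Sensitivity to b.** For 10% versus 0%, the ratio is 0.28/0.20 = 1.40 at b = 20% and 0.46/0.40 = 1.15 at b = 40%. For 25% versus 10%, it is 0.40/0.28 = 1.43 and 0.55/0.46 = 1.20.

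**Patients affected.** With 100 positives, b = 30% and 10% versus 0%, the extra scored patients number 100 × (0.37 − 0.30) = 7.

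**Chance of a spurious finding.** The plan specifies no test of this outcome. If a two-sided 5% comparison of proportions were made with 100 versus 300 patients at b = 30%, it would reject in about 26% of studies for 10% versus 0%, and in about 45% for 25% versus 10% (normal approximation).

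**After the change.** Counting only unplanned admissions returns 0.30/0.30 = 1.0, but by construction, because unplanned risk was set equal in the two groups.

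**The case against.** The strongest reply is that the plan is silent, and silence is not a rule. A reader might infer that the plan states that elective procedures are scored as adverse outcomes. It does not. No section says planned admissions count, and the separate naming of interventions (section 1.1) and device implantation (secondary list) suggests that the authors may see procedures and hospitalisations as different things. This stands as a limit on the wording: the supported statement is that planned admissions are not excluded. It does not remove the problem, because an unqualified term read literally includes them.

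A second reply concerns the AF cohort. A reader might infer that this cohort will look worse than the sinus-rhythm cohort because its rhythm is treated electively. The endpoint and analysis sections of section 7 specify no comparison of outcomes between the cohorts. AF is also not named in the expanded arrhythmia list. Planned admissions for AF already present at entry can occur in arrhythmia-negative patients too: with 100 positives in 400, at least 100 of the 200 AF patients are negative. Such admissions pull the ratio back towards 1. This reply stands in full, and no claim about the AF cohort is made here.

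Third, ratios of 2 or more, with near-certain rejection, can be obtained by assuming that up to half of positives have a planned admission and that no negatives do. Nothing in the documents supports either assumption. The first co-primary endpoint covers medication as well as devices, and starting medication need not mean admission. Admissions for pacing devices would overlap with the separate device item.

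Fourth, restricting to unplanned admissions is not a complete cure. A serious patch finding could itself lead to an unplanned admission. This also stands, and is why the fix asks for a record of whether the patch result prompted the admission.

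Finally, the reach is limited. The sample-size section calls the study a pilot, and the multivariable models name mortality and an undefined composite, not this hospitalisation outcome on its own. Even so, the relationship to hospitalisation is a stated secondary endpoint.

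**Conclusion.** The point holds as a gap in the definition of one secondary endpoint, with a credible route to bias. Planned admissions are not excluded, all admissions are collected, and the exposure leads to treatment. The association is inflated if planned admissions are more frequent in arrhythmia-positive patients, which the link from finding to treatment makes plausible but the documents do not quantify.

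The size rests wholly on the assumed difference in planned rates. At 30% unplanned risk the examples give 1.23 (10% versus 0%) and 1.28 (25% versus 10%); equal rates give no bias, and a higher rate in negatives would reverse it. Mortality and arrhythmia-prevalence results are untouched. The undefined composite in the Secondary endpoint analysis is affected only if it includes this hospitalisation outcome.

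**What to change.** 1. In the Study Summary, section 3.1 and Secondary endpoints, define the outcome as unplanned hospitalisation for heart failure or arrhythmia.
2. For each admission, record from the electronic records already searched under section 10.4: admission type (planned or unplanned), main reason, and whether the patch result prompted it.
3. Report planned admissions separately and descriptively, outside the endpoint. Report patch-prompted admissions separately as well, so that readers can see how many unplanned events followed from detection.
4. Keep the any-admission version as a sensitivity analysis. If the composite in the Secondary endpoint analysis is to include hospitalisation, state that it uses the same definition.

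The cost is a short text change in three places and a few extra data fields, with no added patients or procedures and no change to care. The downside is somewhat fewer events, and so slightly wider intervals, for this one endpoint. The rule should be fixed before the admissions are classified.
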